# 9.10 Management of Toxicity

The study will be monitored continuously for treatment-related adverse events. Expected treatment-related toxicities of ipilimumab will be managed per standard clinical practice and in accord with the package insert for YERVOY® (ipilimumab).

# 9.11 Data Collection

9.11.1 Endpoint Data

- Endpoint data will be collected using HITC IML data forms, participant-specific binders, and the HITC laboratory database.
- The HITC laboratory database, which has password-restricted access, is stored on the UVA Health System Computing Services secured server.

# 9.12 Monitoring Plan

9.12.1 The University of Virginia Cancer Center Data and Safety Monitoring Committee (CC DSMC) will provide oversight of the conduct of this study. The CC DSMC will report to the UVA Protocol Review Committee (PRC).

- 9.12.2 The UVA CC DSMC will review the following:
  - All adverse events
  - Audit results
  - Application of study designed stopping/decision rules
  - Whether the study accrual pattern warrants continuation/action
  - Protocol violations
- 9.12.3 The UVA CC DSMC will meet every month for aggregate review of data. Tracking reports of the meetings are available to the PI for review. Issues of immediate concern by the DSMC are brought to the attention of the sponsor (and if appropriate to the PRC and IRB) and a formal response from the

sponsor is requested. Per the UVA Cancer Center NIH approved institutional plan, this study will be audited approximately every 6 months.

# **10.0 STUDY CONDUCT AND ETHICAL CONSIDERATIONS**

This study will be conducted in compliance with ICH Good Clinical Practice (GCP) Guidelines and in accord with the ethical principles that originated in the Declaration of Helsinki. In addition, all local laws and regulations will apply. The PI will ensure that staff are trained and carry out the study in accord with the protocol specifications.

#### 10.1 UVA Institutional Review Board for Health Sciences Research

The UVA Institutional Review Board for Health Sciences Research (UVA IRB-HSR) will approve all aspects of this study, including the clinical trial protocol, informed consent documents, and patient materials. Modifications to the protocol or consent form will be reviewed and approved by the UVA IRB-HSR prior to implementation, except when necessary to eliminate apparent immediate hazards to the study participants. The study will undergo continuing IRB review based on the level of risk as assessed by the IRB. This review will take place no less than annually. Reporting to the UVA IRB-HSR will occur as specified in Section 9.6.

#### **10.2 Consent Forms and the Consenting Process**

Consent forms will be written in accord with 21 CFR 50 and will be reviewed and approved by the UVA IRB-HSR prior to use. Participants will be given a consent form to review and a member of the study team will be available to answer any questions. Informed consent will be obtained from each participant prior to conducting any study-specific procedures or administering study drug.

#### **10.3 Maintenance of Study Documents**

Signed consent forms and other research records will be retained in a confidential manner. Study records will be kept for at least 6 years after completion of the study.

IRB-HSR# 17780 / IND# 10825 Version Date: 10-10-17

# 11.0 APPENDICES

- Appendix 1: Study Calendar
- Appendix 2: AJCC Staging System
- Appendix 3: ECOG Performance Status
- Appendix 4: New York Heart Association Disease Classification
- Appendix 5: RECIST 1.1 Criteria
- Appendix 6: NCI Common Terminology Criteria for Adverse Events v4
- Appendix 7: Vaccine Lot Release and Stability Testing
- Appendix 8: Summary of Changes

# Appendix 1: Study Calendar

			Active Treatment							Follow-up m						
Studies & Tests	At	Day	1	8	15	22	43	57	64	85	92	FU	FU	FU	FU	FU
	Screening	Week	0	1	2	3	6	8	9	12	13	18	24	27	V4 52	104
Informed consent	Xa															
Pathology review	Xa															
CBC with differential	Xp		Xf			Х	Х		Х	Х					Х	Х
Comprehensive chemistry	X b,e		Xf			Х	Х		Х	Х					Х	Х
HGB-A1C	Xp															
LDH	Xp															
Cortisol			Х			Х	Х		Х							
Free T4			Х			Х	Х		Х							
TSH			Х			Х	Х		Х							
Urinalysis	Xb															
β-HCG	Xc															
HIV / Hepatitis C	Xd															
CT chest/abdomen/pelvis or PET-CT	Xp							х		X h		Xi		х	Xj	Xj
Head MRI / CT	Xp							XI		X h		Xi		Х	Xj	Xj
History & physical	Xp		Xf	Х	Х	Х	Х		Х	Х	Х	Х	Х	Х	Х	Х
Medication Review	Xp		Х	Х	Х	Х	Х		Х	Х	Х	X n	Xn	Xn	Xn	Xn
Record baseline symptoms			Х													
AE assessment				Х	Х	Х	Х		Х	Х	Х	Х	Х	Х	Х	Х
Designation of potential vaccination sites	Xp															
Assessment of skin and nodal basins for evidence of disease	Xp									х				х	х	х
Assessment of skin for vitiligo			Х			Х				Х				Х	Х	Х
Assessment of hair and eye color			Х			Х				Х				Х	Х	Х
Visual acuity exam/ color vision			Х													
120cc green top tubes			X k													
80cc green top tubes				Х	Х	Х	Х		Х	Х	Х	Х	Х	Х	Х	Х

			Active Treatment									Follow-up m				
Studies & Tests	At Screening	Day	1	8	15	22	43	57	64	85	92	FU v1	FU v2	FU v3	FU v4	FU v5
		Week	0	1	2	3	6	8	9	12	13	18	24	27	52	104
20cc red top tubes			Х	Х	Х	Х	Х		Х	Х	Х	Х	Х	Х	Х	Х
Anti-nuclear antibody / Rf factor			Х						Х						Х	Х
Vaccination with 6MHP			Х	Х	Х		Х		Х	Х						
Tumor biopsy g			Х			Х										
Sentinel immunized node biopsy						Х										
Participant diary reviewed and/or distributed			х	х	х	х	х		х	х	х	Х				
ipilimumab: 3 mg/kg IV			Х			Х	Х		Х							

a Any point prior to registration

b Pre-study within 6 weeks of registration

c Within 2 weeks of registration (for childbearing women)

d Within 6 months of registration

e To include fasting glucose

f History & physical, comprehensive chemistry, and CBC with differential scheduled for Day 1 are not required if prestudy assessments were within 10 calendar days of day 1. However, hair and eye color assessment and assessment of skin for vitiligo should be performed if theses assessments were not completed as part of the pre-study visit. gFor patients who have tumor accessible to biopsy, biopsies will be completed 1) during screening or, once enrolled, prior to treatment on Day 1, and 2) at day 22, for subjects who have melanoma available for biopsy. Additional optional biopsies may be performed for research purposes during the study or during follow-up if participants are removed from the study or experience progression. If surgical resection or biopsies are completed for clinical care, the tumor tissue may be collected for study related analyses.

h Tumor imaging at day 85 should be performed only when clinically needed to verify objective clinical responses at day 57.

If scans were completed at day 85, the scans do not have to be repeated at this visit.

 Scans do not need to be repeated for the protocol if they have been performed recently (typically within 3 months).

kBlood for HLA typing is included in the research bloods.

Required only for subjects with brain metastases.

mFollow-up visits in the initial follow-up phase will occur as follows: FUv1: 42 days from the last dose of 6MHP; FUv2 = 24 weeks from the first dose of 6MHP; FUv3 = 27 weeks from the first dose of 6MHP; FUv4 = 1 year from the first dose of 6MHP; FUv5 = 2 years from the first dose of 6MHP.

nOnly information about anticancer therapy will be collected

T Classification	Thickness	Ulceration Status						
τ.	< 1.0 mm	a: without ulceration or mitoses						
	S 1.0 mm	b: with ulceration or mitoses $\geq 1$						
Т2	1.01 2.0 mm	a: without ulceration						
12	1.01 – 2.0 mm	b: with ulceration						
Т2	2.01 4.0 mm	a: without ulceration						
15	2.01 – 4.0 mm	b: with ulceration						
Тл	> 1 0 mm	a: without ulceration						
14	24.01111	b: with ulceration						

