6.5.1 Dose Delays Due to Toxicity

- In circumstances where assessment of an AE is limited, such as by intercurrent illness, or when laboratory studies are required to assess for other causes of toxicity, the vaccine schedule may be interrupted for up to 21 days. Delay of one vaccine administration by up to 21 days will not be considered a protocol violation if due to an AE, regardless of attribution. If more than one vaccine is delayed by 21 days due to an AE, regardless of attribution, vaccine treatment should be discontinued, though the other systemic therapy may be continued.
- Dose delays for ipilimumab will follow standard clinical guidelines.

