### 6.5.2 Delayed Visits for Reasons Other Than Toxicity

A schedule for return visits should be established at the first visit. If a participant misses a treatment, the missed treatment will be administered as soon as possible, so that subsequent treatments will be given in the appropriate intervals. Treatment may be continued for an additional time period, if needed. Participants who are treated outside of the established schedule should return to the original schedule as soon as possible

The table below (Table 7) defines what constitutes a delayed visit, whether the participant should continue to be treated, and whether a protocol violation should be reported and recorded. The range of days is counted from the original scheduled date.

Table 7. Delayed Visit for Reasons other than Toxicity				
Treatment Period	Range of Days	Participant Treatment	Protocol Deviation	
Vaccine 1*/Ipilimumab 1				
Day 1	± 2 days	Vaccine, Labs, Ipilimumab	No	
	$\pm$ 3 to 7 days	Vaccine, Labs, Ipilimumab	Yes	
	$\pm$ 8 or more days	Labs	Yes	
Vaccines 2-3*				
Days 8, 15	± 2 days	Vaccine/Labs	No	
	$\pm$ 3 to 7 days	Vaccine/Labs	Yes	
	$\pm$ 8 or more days	Labs	Yes	
Biopsy/Ipilimumab 2				
Day 22	± 2 days	Labs, Biopsies, Ipilimumab	No	
	$\pm$ 3 to 7 days	Labs, Biopsies, Ipilimumab	Yes	
	$\pm$ 8 or more days	Labs	Yes	
Vaccine 4*/Ipilimumab 3				

Davs 43	± 2 days Vaccine, Labs, Ipilimuma		No
	$\pm$ 3 to 7 days	Vaccine, Labs, Ipilimumab	Yes
	± 8 or more davs	Labs	Yes
Assessment			
Day 57	±7 days	Scans**	No
	$\pm$ 8 to 14 days	Scans	Yes
	$\pm$ 15 or more days	Scans	Yes
Vaccine 5*/Ipilimumab 4			
Day 64	± 7 days	Vaccine, Labs, Ipilimumab	No
	$\pm$ 8 to 14 days	Vaccine, Labs, Ipilimumab	Yes
	$\pm$ 15 or more days	Labs	Yes
Vaccine 6*			
Day 85	± 7 days	Vaccine, Labs, Scans**	No
	$\pm$ 8 to 14 days	Vaccine, Labs, Scans**	Yes
	$\pm$ 15 or more days	Labs/Scans	Yes
Assessment			
Day 92	± 7 days	Labs	No
	$\pm$ 8 to 14 days	Labs	Yes
	$\pm$ 15 or more days	Labs	Yes
Follow-up			
FUv1 and FUv2	± 14 days	Labs/Scans**	No
	$\pm$ 15 or more days	Labs/Scans	Yes
– "			ļ
Follow-up			
FUv3, FUv4, FUV5	$\pm$ 28 days	Labs/Scans**	No
	$\pm$ 29 or more days	Labs/Scans	Yes

\* A participant will be taken off protocol treatment if more than one vaccination is delayed [± 3 to 7 days] during the treatment period.

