# 7.0 CLINICAL AND LABORATORY EVALUATIONS
The following evaluations will be performed on an outpatient basis. Please refer to the study calendar (Appendix 1) for scheduling.

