# 8.5 Safety Monitoring

Toxicities will be monitored using CTCAE 4.03 criteria, with a focus on recording immune-related adverse events (irAE) (9). Stopping rules will be based on an expected irAE rate of 15-20%, where 10-15% had grade 3-4 irAE in one study (38) and in another 19% had grade 3, and 3.2% grade 4 irAEs (59). Significant increases over these rates are not expected but would be a reason for early discontinuation. Thus, formal safety bounds based upon the observed number of participants who experience a DLT as defined in Section 9.9 will guide decisions about early stopping due to potential safety concerns (Table 8). The definition of

DLT considers both irAEs and previously reported DLTs related to vaccine. If a stopping bound is crossed then accrual to the study will be suspended until the study PI, co-investigators and the DSMC can review the data, and determine if the study should continue, be amended or be closed to further accrual. The rate of DLTs will be monitored up to 30 days after the last vaccination. A sequential probability ratio test (SPRT) based upon a binomial test of proportions for DLTs will be used. Only the upper boundary will be used for monitoring to protect against excessive failure rates. The stopping boundary are for a SPRT contrasting a 15% versus 30% DLT rate, with nominal type I and II errors of 10% and 10%, respectively. The slope of the parallel lines for monitoring is 0.219 and the intercept for the upper bound is 2.476.

•	ie o. Otopping Oulde	
	Number of participants	Boundary
	4-6	≥4
	7-11	≥ 5
	12-15	≥6
	16-20	≥7
	21-25	≥ 8
	26-27	≥ 9

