#### 9.4.2 Time Span for Reporting Adverse Events

Reporting of AEs will begin when the participant is administered the study drug or has a study related biopsy. Events occurring through 30 days after administration of the last dose of 6MHP vaccine or ipilimumab, regardless of attribution, will be reported. AEs should be followed to resolution or stabilization. If an AE worsens and becomes an SAE, it should be reported as serious per the guidelines specified for SAE reporting.

AEs that are possibly, probably, or definitely related to any of the study drugs will be recorded until the participant completes treatment follow-up. If, during treatment follow-up, the participant receives an alternative anti-cancer treatment, participants will be off treatment follow-up and will be followed yearly for disease progression and survival.

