	14) Section 3.1.4 Revised inclusion criteria for subjects who have had brain
	metastases
	15) Section 3.2.4.2 Revised inclusion criteria to specify that subjects may
	have previously received CTLA-4 blocking antibody either as

	monotherapy or as part of combination CTLA-4/PD-1 blockade
	participants who have another cancer diagnosis for any cancer without
	distant metastasis that has been treated successfully, without evidence
	of recurrence or metastasis for over 2 years instead of over 3 years.
	17) Section 8.4 changed section name from "Stratification" to "Cohort and
	Post Entry Classification"
	18) Appendix 1 Study Calendar by deleting Comprehensive Chemistry and
	CBC with differential from Day 8 and Day 15
0.7.00.40	19) Updated Reference list
05-06-16	1) Updated signature page
	2) Updated personnel list.
	
 
A) Editorial corrections made throughout document
 

	5) Section 3.2.13: revised to change 5 years to 3 years for exclusion
	criterion related to other cancer diagnoses
	6) Schema Table 7 Section 9.7.1 Appendix 1: replaced Days 127, 269
	190, 365, 730 with FUv1, FUv2, FUv3, FUv4, and FUv5, respectively.
	7) Section 6.2.1: Revised wording to specify that vaccines 4-6 will be
	administered at a separate site than vaccines 1-3 and that vaccines 4-6 will
	be administered at the same site and not rotated.
	8) Section 6.2.4: revised to specify that the vaccine should be
	administered within 1-2 hours after mixing.
	9) Section 6.6.1: this section has been added to clarify the procedures for
	safety follow-up visits.
	10) Section 9.7.1: revised section and moved corrected text to section
	11) Appendix 1: Added CBC and comp chemistry labs to Days 8 and 15.
	recent changes are at the ten of the list
09-10-15	1) Undated Investigator's Agreement to match undated protocol template
00 10 10	2) Updated Study Personnel
	3) Updated Header and Table of Contents
	4) Section 3.2.4.1: Updated exclusion criteria to allow subjects who have
	received a prior PD-1 blocking antibody to be enrolled 3 weeks after
	receiving the last dose of that antibody. This decrease in the waiting
	period from 6 weeks to 3 weeks following the last dose of PD-1 blocking
	antibody is considered a sufficient wash-out period by the clinicians.
	5) Section 3.2.4.2: Updated exclusion criteria to specify in which instances
	prior treatment with a CTLA-4 blocking antibody is considered to be
	exclusionary. The rationale for the change is to broaden the entry
	CTLA 4 thereasy

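### Appendix 1 schedules no CBC or chemistry in the 30 days after vaccine 6; adding both panels at the existing day 92 visit is a cheap improvement

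*Combined protocol and SAP*

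**What the plan says.** The Appendix 1 rows for "CBC with differential" and comprehensive chemistry carry marks at screening, days 1, 22, 43, 64 and 85, and weeks 52 and 104 (FUv4, FUv5). Both are blank at day 92 and at FUv1-FUv3. Vaccines are given on days 1, 8, 15, 43, 64 and 85 (section 6.2.1), and ipilimumab on days 1, 22, 43 and 64 (Synopsis, Treatment Regimen).

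On safety follow-up, section 8.5 says: "The rate of DLTs will be monitored up to 30 days after the last vaccination". Section 9.4.2 requires reporting, whatever the attribution, of "Events occurring through 30 days after administration of the last dose of 6MHP vaccine or ipilimumab".

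At day 92 the calendar has history and physical, medication review, AE assessment, diary review and research blood, but no clinical panel. Footnote m places the next visit at "FUv1: 42 days from the last dose of 6MHP".

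Table 7 (section 6.5.2) gives *Labs* as the day 92 action without defining the term. On visit windows it says: "The range of days is counted from the original scheduled date". Section 6.5.1 adds: "Delay of one vaccine administration by up to 21 days will not be considered a protocol violation if due to an AE". For scheduling of evaluations, section 7.0 says: "Please refer to the study calendar".

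**The concern.** Safety judged by adverse event assessment is a primary objective (section 2.1). Section 9.7.1 relies on laboratory tests to pick up toxicities that the history and examination miss, and section 9.8 lists the values to be graded, including hemoglobin, white cells, transaminases, bilirubin and creatinine.

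A cytopenia or a rise in transaminases or creatinine that causes no symptoms is found only if someone draws blood. After vaccine 6 the calendar requires no such draw until week 52. Such a change would therefore surface only through symptom-prompted or routine-care testing. The day 85 panel belongs to the vaccine 6 visit itself, so it cannot serve as a check after that dose.

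**Working it through.** **1. The plan's own timing.** FUv1 is 42 days after the last vaccine: 85 + 42 = day 127, and (127 - 1)/7 = 18 weeks. This matches the week 18 column, so the nominal days are consistent.

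**2. Panels after vaccine 6.** The 30 days end at 85 + 30 = day 115. Week 52 is 1 + 52 × 7 = day 365. Scheduled panels in days 86-115: **0**. Gap to the next panel: 365 - 85 = **280 days**.

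**3. Comparison with the other vaccines (nominal days).**

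| Vaccine | Day | Next panel at a later visit | Interval (days) |
|---|---|---|---|
| 1 | 1 | 22 | 21 |
| 2 | 8 | 22 | 14 |
| 3 | 15 | 22 | 7 |
| 4 | 43 | 64 | 21 |
| 5 | 64 | 85 | 21 |
| 6 | 85 | 365 | 280 |

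**4. What is covered.** The last ipilimumab dose is day 64, and its 30 days end on day 94. The day 85 panel falls 21 days after that dose and after vaccine 5.

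**5. Visits available.** Day 92 is the only nominal visit in days 86-115. FUv1 has ±14 days in Table 7, so it can fall 42 - 14 = 28 to 42 + 14 = 56 days after vaccine 6. It can just enter the 30 days, but it has no CBC or chemistry mark either.

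**6. Whether *Labs* in Table 7 fills the gap.** Table 7 also lists *Labs* at FUv1-FUv3, where the calendar marks only research tubes, and section 7.0 makes the calendar the schedule. The word alone does not establish a CBC or chemistry.

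**7. Why a bare mark at day 92 is not enough.** Without a deviation, vaccine 6 may be given on days 78-92 (85 ± 7) and the day 92 visit may occur on days 85-99 (92 ± 7). The visit then falls between 85 - 92 = **-7** and 99 - 78 = **+21** days relative to the dose. A permitted AE delay moves vaccine 6 to 85 + 21 = day 106, which is 14 days after nominal day 92.

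**8. Illustration of size.** Table 3 (n = 207, vaccine trials) lists related grade 3-4 events visible on these panels: hemoglobin 0.5 + lymphopenia 1 + AST 0.5 + ALT 1 + bilirubin 0.5 = 3.5%, if no patient had two. For 27 participants over the whole course, 27 × 0.035 = 0.945. The documents do not say when events occur. If 1/6 followed vaccine 6, that is 0.16 participants; with a share from 1/12 to 1/3, it is 0.08 to 0.32. These are not ceilings, because ipilimumab laboratory events are left out. Nor are they all gain, because some events would be found anyway.

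**9. Stopping rule.** The section 8.5 constants reproduce. With D = ln[(0.30 × 0.85)/(0.15 × 0.70)] = 0.887, the slope is ln(0.85/0.70)/D = 0.219 and the intercept is ln(0.9/0.1)/D = 2.476. The bound is 2.476 + 0.219 × 24 = 7.73, so 8 DLTs, at 24 participants, and 2.476 + 0.219 × 27 = 8.39, so 9, at 27. Both agree with Table 8.

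**The case against.** The strongest reply is that the schedule looks deliberate and the consequence is small. The vaccine was well tolerated in about 200 patients (section 1.5), and direct peptide toxicity is not expected (section 1.7). The summary of changes (05-18-17) removed both panels from days 8 and 15, which are also 7 days after a vaccine. Other capture exists: examination, AE assessment and diary review at day 92; routine-care results under section 9.8; and related AEs through treatment follow-up under section 9.4.2.

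Much of this stands, and it limits the point to silent laboratory changes. It does not explain the gap. The panels dropped from days 8 and 15 are backed by day 22, while nothing comparable follows vaccine 6.

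One could also answer that *Labs* at day 92 already means a clinical panel, and that the same word at days 8 and 15 is left over from when panels were drawn there. That is possible for days 8 and 15. It does not account for FUv1-FUv3, so the term needs a definition in any case.

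A reader might infer something stronger: that no panel falls anywhere in the AE and DLT monitoring period, or that ipilimumab toxicity goes unmonitored. The documents do not support this. Reporting starts with the first study drug or study biopsy, so the panels at days 22, 43, 64 and 85 lie inside the period, and day 85 is within 30 days of the last ipilimumab dose.

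**Conclusion.** The point holds as a modest design improvement, not as an error in a stated figure. On nominal days there are 0 scheduled CBC or chemistry panels in the 30 days after vaccine 6, and the next comes about 280 days after it, against 7-21 days for vaccines 1-5.

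The number of events that an added panel would find cannot be derived from the documents without assuming when events occur, so the figures in step 8 are illustrative only.

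A reader might also infer that the DLT stopping rule is compromised. That does not follow. An ipilimumab DLT needs permanent discontinuation, and the last planned dose is day 64. A vaccine DLT must be unexpected. Section 9.1.2 would make the laboratory events in Table 3 expected, although the 4% rule in section 1.5 and Table 4 would leave high-grade ones unexpected. Even on that second reading the likely numbers are small against bounds of 8-9 DLTs at 21-27 participants. No stopping decision is expected to change. The reason to act is better AE ascertainment and patient safety at very low cost.

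**What to change.** - **Appendix 1:** mark CBC with differential and comprehensive chemistry at the existing day 92 visit.
- **New footnote:** *This panel must be drawn after the last 6MHP dose actually given, about 7 days and no later than 30 days after it. If the day 92 visit falls before that dose or outside this period, or if vaccine is stopped early, use a panel from another scheduled or routine-care visit within the 30 days.*
- **Table 7:** state that *Labs* means the tests marked in Appendix 1 for that visit.
- **Leave the day 92 research-blood timing as it is.** The primary immune endpoint needs two consecutive responses (section 8.2.2), and there is no reason to move those samples for a safety panel.

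The cost is one extra panel per participant: 0.3 ml CBC + 0.9 ml chemistry = 1.2 ml (section 7.4), at a visit that already draws 80 + 20 = 100 ml. No visit is added for participants on schedule. After a draw on day 92, days 93-115 would still rely on clinical follow-up and routine-care results.
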